#### Definition of Bleeding Complications

##### MVARC Primary Bleeding Scale\*

###### I. Minor

Any overt,† actionable sign of hemorrhage (e.g., more bleeding than would be expected for a clinical circumstance, including bleeding found by imaging alone) that meets  $\geq 1$  of the following: requiring nonsurgical medical intervention by a health care professional; leading to hospitalization or increased level of care; prompting evaluation; or requires 1 or 2 U of whole blood or packed RBC transfusion and otherwise does not meet criteria for major, extensive, or life-threatening bleeding.

Medtronic Business Restricted

**CONFIDENTIAL**

056-F275, vC Clinical Investigation Plan Template

# The Early Feasibility Study of the Intrepid™ TMVR Transseptal System Clinical Investigation Plan

Version 4.0

Page 76 of 102

Medtronic

## Definition of Bleeding Complications

### II. Major

Overt bleeding either associated with a drop in the hemoglobin of  $\geq 3.0$  g/dl‡ or requiring transfusion of  $\geq 3$  U of whole blood or packed RBCs AND does not meet criteria of life-threatening or extensive bleeding.

### III. Extensive

Overt source of bleeding with drop in hemoglobin of  $\geq 4$  g/dl‡ or whole blood or packed RBC transfusion  $\geq 4$  U within any 24-h period, or bleeding with drop in hemoglobin of  $\geq 6$  g/dl‡ or whole blood or packed RBC transfusion  $\geq 4$  U (BARC type 3b) within 30 days of the procedure.

### IV. Life-threatening

Bleeding in a critical organ, such as intracranial, intraspinal, intraocular, or pericardial necessitating surgery or intervention, or intramuscular with compartment syndrome OR bleeding causing hypovolemic shock or hypotension (systolic blood pressure  $<90$  mm Hg lasting  $>30$  min and not responding to volume resuscitation) or requiring significant doses of vasopressors or surgery.

### V. Fatal

Bleeding adjudicated as being a proximate cause of death. Severe bleeding adjudicated as being a major contributing cause of a subsequent fatal complication, such as MI or cardiac arrest, is also considered fatal bleeding.

## Modified BARC Bleeding Scale (Secondary Use)§

### Type 0

No Bleeding.

### Type 1

Bleeding that is not actionable and does not cause the patient to seek unscheduled performance of studies, hospitalization, or treatment by a health care professional. May include episodes leading to self-discontinuation of medical therapy by the patient without consulting a health care professional.

### Type 2

Any overt,† actionable sign of hemorrhage (e.g., more bleeding than would be expected for a clinical circumstance, including bleeding found by imaging alone) that does not fit the criteria for type 3, 4, or 5 but does meet  $\geq 1$  of the following: requiring nonsurgical medical intervention by a health care professional, leading to hospitalization or increased level of care, or prompting evaluation.

Medtronic Business Restricted

CONFIDENTIAL

056-F275, vC Clinical Investigation Plan Template

# The Early Feasibility Study of the Intrepid™ TMVR Transseptal System Clinical Investigation Plan

Version 4.0

Page 77 of 102

Medtronic

## Definition of Bleeding Complications

### Type 3a

- Overt\* bleeding plus hemoglobin drop of 3 to  $<5$  g/dl‡ (provided drop is related to bleed)
- Any transfusion with overt bleeding

### Type 3b

- Overt bleeding plus hemoglobin drop  $\geq 5$  g/dl‡ (provided drop is related to bleed)
- Cardiac tamponade
- Bleeding requiring surgical intervention for control (excluding dental/nasal/skin/hemorrhoid)
- Bleeding requiring IV vasoactive agents

### Type 3c

- Intracranial hemorrhage (does not include microbleeds or hemorrhagic transformation but does include intraspinal bleeding)
- Subcategories confirmed by autopsy, imaging, or lumbar puncture
- Intraocular bleeding compromising vision

### Type 4 (periprocedural)

- Perioperative intracranial bleeding  $\leq 48$  h
- Reoperation after closure of incision site for the purpose of controlling bleeding
- Transfusion of  $\geq 5$  U whole blood or packed RBCs within 48 h period of the index procedure
- Chest tube output  $\geq 2$  l within 24 h period

### Type 5a

Probable fatal bleeding. No autopsy or imaging confirmation but clinically suspicious.

### Type 5b

Definite fatal bleeding. Overt bleeding, autopsy, or imaging confirmation.

\* Modified with permission from VARC-2 (29).

† “Overt” bleeding is defined by any of the following criteria being met: Reoperation after closure of sternotomy for the purpose of controlling bleeding; chest tube output  $>2$  l within any 24 h period,  $>350$  ml within the first post-operative hour,  $\geq 250$  ml within the second post-operative hour, or  $>150$  ml within the third post-operative hour; or visible bleeding from the vascular system either at or remote from the access/surgical site.

‡ Adjusted for the number of units of blood transfused (1 U packed red blood cells or whole blood is equivalent to 1 g/dl hemoglobin).

§ Modified from BARC.

BARC = Bleeding Academic Research Consortium; IV = intravenous; MVARC = Mitral Valve Academic Research Consortium; RBC = red blood cells; VARC = Valve Academic Research Consortium.

## 17.1.7 BUNDLE BRANCH BLOCK

ACC/AHA/HRS 2006 Key Data Elements and Definitions for Electrophysiological Studies and Procedures; A Report of the American College of Cardiology/ American Heart Association Task Force on Clinical Data Standards (ACC/AHA/HRS Writing Committee to Develop Data Standards on Electrophysiology); JACC, 2006 (15).

Medtronic Business Restricted

CONFIDENTIAL

056-F275, vC Clinical Investigation Plan Template

**Left Bundle Branch Block (LBBB)**

- QRS duration 120 ms or longer
- Delayed onset of intrinsicoid deflection in I, V5, and V6  $>60$  ms
- Broad and notched or slurred R waves in I, aVL, V5, and V6
- rS or QS complexes in right precordial leads
- ST-segment and T waves in opposite polarity to the major QRS deflection

**Right Bundle Branch Block (RBBB)**

- QRS duration  $\geq 120$  ms
- rsR' or rSR' complexes in V1 and V2
- Delayed onset of intrinsicoid deflection in V1 and V2  $>50$  ms
- Broad, slurred S wave in I, V5, and V6
- Secondary ST-T wave changes

**17.1.8 CARDIAC STRUCTURAL COMPLICATION-NON-ACCESS SITE RELATED**

- Major cardiac structural complications, including:
  - Cardiac perforation\* or pseudoaneurysm resulting in death, life-threatening bleeding, hemodynamic compromise, or tamponade, or requiring unplanned surgical or percutaneous intervention
- Minor cardiac structural complications, including:
  - Cardiac perforation\* or pseudoaneurysm not meeting major criteria

\*including the left ventricle, left atrium, coronary sinus, right atrium and right ventricle

**17.1.9 CARDIAC PERFORATION**

A laceration or tearing of the walls of the ventricles or atria of the heart; of the interatrial or interventricular septum; of the papillary muscles or chordae tendineae; or of the one of the valves of the heart.

**17.1.10 CARDIAC TAMPONADE**

Clinical syndrome caused by the accumulation of fluid in the pericardial space, resulting in reduced ventricular filling and subsequent hemodynamic compromise.

**17.1.11 CARDIOGENIC SHOCK**

Cardiogenic shock will be defined as modified from the 2017 AHA Scientific Statement: Contemporary Management of Cardiogenic Shock

Cardiac disorder that results in tissue hypoperfusion as supported by:

*Medtronic Business Restricted*

**CONFIDENTIAL**

056-F275, vC Clinical Investigation Plan Template

- Systolic BP<90 mmHg for  $\geq$ 30 minutes  
**OR**
- Cardiac Index of  $\leq$ 1.8 L/min/m^2 and PCWP  $\geq$ 15mmHg  
**OR**
- Intervention with pharmacological or mechanical support to maintain systolic BP  $\geq$ 90 mmHg;

**AND**

- End-organ hypoperfusion documented by:
  - Urine output <30 mL/h, **or**
  - Cool extremities, **or**
  - Clinical pulmonary congestion, **or**
  - Altered mental status, **or**
  - Lactate >2.0 mmol/L

**OR**

- Death

Timing will be characterized as pre-operative, intra-operative (in the operating room), or post-operative (operating room discharge through 30 days).

Notes:

- Excluding prophylactic use of pharmacological or mechanical support
- Unless directly attributed to another medical condition

## 17.1.12 CHRONIC RENAL INSUFFICIENCY

Kidney damage or glomerular filtration rate (GFR) <60 mL/min/1.73 m^2 for  $\geq$ 3 months.

Kidney damage is defined as pathologic abnormalities or markers of damage, including abnormalities in blood or urine test or imaging studies.

## 17.1.13 CONVERSION TO OPEN MITRAL VALVE SURGERY DURING A TRANSCATHETER PROCEDURE

Conversion to open mitral valve surgery will be defined and classified according to the Mitral Valve Academic Research Consortium (MVARC); Clinical Trial Design Principles and Endpoint Definitions for Transcatheter Mitral Valve Repair and Replacement: Part 2: Endpoint Definitions; JACC, 2015 (14).

Subclassified as:

- Secondary to mitral valve apparatus damage or dysfunction, requiring surgical valve repair or replacement, or
- Secondary to procedural complications (such as cardiac perforation, removal of an embolized device, and so on)

#### **17.1.14 CORONARY VESSEL COMPRESSION OR OBSTRUCTION**

Coronary vessel compression or obstruction will be defined and classified according to the Mitral Valve Academic Research Consortium (MVARC); Clinical Trial Design Principles and Endpoint Definitions for Transcatheter Mitral Valve Repair and Replacement: Part 2: Endpoint Definitions; JACC, 2015 (14).

Angiographic evidence of any reduction in coronary artery luminal diameter or coronary sinus diameter due to either external compression, thrombosis, embolism, dissection, or other cause, subclassified as:

- Major ( $\geq 50\%$  diameter stenosis) or minor ( $< 50\%$ )
- Symptomatic or not
- Requiring treatment or not
- Transient (intraprocedural only, resolved at procedure end) or persistent

#### **17.1.15 DAMAGE TO THE NATIVE MITRAL VALVE APPARATUS**

Damage to the native mitral valve apparatus will be defined and classified according to the Mitral Valve Academic Research Consortium (MVARC); Clinical Trial Design Principles and Endpoint Definitions for Transcatheter Mitral Valve Repair and Replacement: Part 2: Endpoint Definitions; JACC, 2015 (14).

- Chords
- Papillary muscles
- Leaflets
- Mitral annulus

#### **17.1.16 DEEP WOUND INFECTION**

Deep Wound Infection will be defined and classified according to The Society of Thoracic Surgeons' (STS).

Online Risk Calculator: Risk Model and Variables – STS Adult Cardiac Surgery Database Version 2.81.

Deep sternal wound infection or mediastinitis (per CDC definition) diagnosed within 30 days of the operation or any time during the hospitalization for the Index Procedure.

## 17.1.17 DEVICE FRACTURE

Device fracture will be defined and classified according to the Mitral Valve Academic Research Consortium (MVARC); Clinical Trial Design Principles and Endpoint Definitions for Transcatheter Mitral Valve Repair and Replacement: Part 2: Endpoint Definitions; JACC, 2015 (14).

- Major: a break, tear, perforation, or other structural defect in the device (stent, housing, leaflet, arm, and so on) resulting in device failure, resulting in recurrent symptoms, or requiring reintervention, or
- Minor: a break, tear, perforation, or other structural defect in the device (stent, housing, leaflet, arm, and so on) not resulting in device failure, not resulting in recurrent symptoms, and not requiring reintervention

Device fracture will be further classified as follows:

- Primary: a break, tear, perforation, or other structural defect in the device (stent, housing, leaflet, arm, and so on) in the absence of canting, malposition, migration or rocking motion, or
- Secondary: a break, tear, perforation, or other structural defect in the device (stent, housing, leaflet, arm, and so on) resulting from an unintended loading and strain when an implant functions in abnormal conditions due to canting, malposition, migration or rocky rocking motion

## 17.1.18 DEVICE MIGRATION AND MALPOSITIONING

- Device Malposition: Intrepid valve is deployed in a location other than intended
- Migration with incomplete detachment: after initially correct transcatheter implantation of the Intrepid valve at the level of the mitral valve annulus, the device moves towards left atrium or left ventricle but stays partially or completely attached to the annulus.
- Migration with complete detachment: after initially correct transcatheter implantation of the Intrepid valve at the level of the mitral valve annulus, the device moves towards left atrium or left ventricle and completely loses its contact with the annulus.

## 17.1.19 DEVICE THROMBUS

Device thrombus will be defined as any thrombus attached to or near an implanted valve and will be subclassified as:

- *Clinically significant valve thrombosis*: visualization of thrombus by echo or by MDCT (including HALT  $\geq 50\%$ ) and evidence of arterial embolism or new/worsening heart failure.
- *Significant thrombosis without clinical sequelae*: visualization of thrombus by echo or by MDCT (including HALT  $\geq 50\%$ ) in the absence of arterial embolism or new/worsening heart failure, meeting criteria of significant increase in mean gradient

# The Early Feasibility Study of the Intrepid™ TMVR Transseptal System Clinical Investigation Plan

Version 4.0

Page 82 of 102

Medtronic

across the implant\* and warranting initiation or intensification of systemic anticoagulation.

- *Subclinical thrombosis*: visualization of thrombus by echo or by MDCT (including HALT  $\geq 50\%$ ) in the absence of arterial embolism or new/worsening heart failure and not meeting criteria of significant increase in mean gradient across the implant\*.

If thrombus is discovered on the implant at autopsy, it will be considered *clinically significant with clinical sequelae* if there was evidence of arterial embolism or new/worsening heart failure diagnosed ante- or postmortem. In the absence of arterial embolism or new/worsening diagnosed ante- or postmortem, thrombosis will be considered *significant without clinical sequelae* if last available echo met criteria of significant increase in mean gradient across the implant\* and *subclinical* if last available echo does not meet criteria of significant increase in mean gradient across the implant\*.

\*trans-mitral mean  $\Delta \geq 6$  mmHg AND  $\geq 5$  mmHg increase from discharge (10)

The definition of **Worsening Heart Failure** is related to the valve thrombosis events. For Heart Failure admissions, please refer to **Hospitalization** subclassified as Heart Failure.

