### **9.20.3 Subject Death**

In the event that a subject dies after implantation of the TMVR bioprosthesis, the Investigator will make reasonable effort to have an autopsy performed to help determine the extent to which the subject's death was related to the device/procedure. If possible, the TMVR bioprosthesis will be explanted and returned to the Sponsor. Contact your Medtronic representative to obtain instructions for proper return of the device.

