## Definition of Worsening Heart Failure\*

### Presence of both:

#### I. New or progressive symptoms/signs of decompensation heart failure

- History
  - Significant weight gain
  - Worsening dyspnea
  - Worsening fatigue
- Physical Examination
  - Newly elevated jugular venous pressure
  - New cardiac S3 gallop rhythm
  - New pulmonary rales
  - New hepatic congestion
  - New peripheral edema
  - New development of cool extremities

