#### II. Unplanned intensification of decongestive therapy in response to progressive symptoms/signs of heart failure:

- Oral
  - Increased dose of loop diuretic
  - Addition of thiazide diuretic to loop diuretic
- Intravenous administration of diuretic

\* Mallick et al. PROSPECT Trial. J Am Coll Cardiol HF 2016;4:749–55

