### 17.1.27 INTERACTION WITH NON-MITRAL VALVE INTRACARDIAC STRUCTURES

Interaction with non-mitral- valve intracardiac structures will be classified as

- Left ventricular outflow tract obstruction:
  - Visual narrowing of the LVOT tract AND
  - Peak LVOT jet velocity  $\geq 2.7$  m/s (peak instantaneous gradient  $\geq 30$  mmHg) measured by CW Doppler under basal (resting) conditions or physiologically provoked (Valsalva maneuver or post premature ventricular contraction) AND
  - An increment in peak LVOT gradient  $\geq 10$  mm Hg from baseline
  - Additional notes and considerations:
    - LVOT obstruction will be considered severe if peak LVOT jet velocity  $\geq 3.5$  m/s (peak instantaneous gradient  $\geq 50$  mm Hg).
    - **Non-severe:** Peak LVOT jet velocity greater than or equal to 2.7 ms/s to 3.4 m/s (peak instantaneous gradient  $\geq 30$  mm Hg)
    - **Non-event:** Less than 2.7 m/s peak LVOT jet velocity
    - All cases with peak LVOT jet velocity  $\geq 2.7$  m/s (peak instantaneous gradient  $\geq 30$  mm Hg) measured by CW Doppler will be submitted to the CEC for adjudication.
    - AEs/SAEs related to *intraprocedural* increase in LVOT gradient will be submitted to the CEC for adjudication. Cases of intraprocedural LVOTO resulting into death or explant will be considered severe LVOTO.
    - Cases of LVOTO resulting into septal reduction therapy (alcohol septal ablation or septal myectomy) will be considered severe LVOTO.
    - Cases of LVOTO incidentally discovered by pathology will be assessed based on the last available peak LVOT jet velocity measured by CW Doppler; any attempt should be done to submit this last echo to the Echo Core Lab and to the CEC. Alternatively, the last follow-up echo Core Lab CW measurements will be used to define LVOTO.

Outflow Tract Gradient Severity Scale CW Doppler			
	Mild	Moderate	Severe
Velocity m/sec	$\geq 2.7$ -3.1	3.2 - 3.4	$\geq 3.5$
Peak Gradient mmHg	$\geq 30$ -39	40 - 49	$\geq 50$

- Aortic valve regurgitation ( $\geq$  moderate or 2+)
- Other

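### The autopsy rule for device thrombus ignores a finding that the thrombus caused the death, so in a narrow case a fatal valve thrombosis is classed as subclinical

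*Combined protocol and SAP*

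**What the plan says.** EFS CIP Section 17.1.19 has three device-thrombus classes: clinically significant, significant without clinical sequelae, and subclinical. In general the top class needs visible thrombus plus "evidence of arterial embolism or new/worsening heart failure".

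For thrombus discovered on the implant at autopsy there is a separate rule:

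- Top class: "if there was evidence of arterial embolism or new/worsening heart failure diagnosed ante- or postmortem".
- Failing that, the middle class if the last available echo met the gradient criterion: a mean transmitral gradient of at least 6 mmHg and a rise of at least 5 mmHg since discharge.
- Failing that, subclinical, "if last available echo does not meet criteria of significant increase in mean gradient across the implant".

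The section also defines worsening heart failure for thrombosis events. That definition requires "Presence of both" of two parts. The first is new or progressive symptoms or signs. The second is "Unplanned intensification of decongestive therapy in response to progressive symptoms/signs of heart failure". New heart failure, as distinct from worsening, has no definition of its own.

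Deaths are handled elsewhere. Section 9.20.3 asks for reasonable effort to obtain an autopsy "to help determine the extent to which the subject's death was related to the device/procedure". Section 11.6.1 gives the CEC the final adjudication of cause of death. Section 17.1.32 lists thromboembolism and device failure among the cardiovascular causes. No text carries that result back to the thrombus class.

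**The concern.** The autopsy rule applies to people who have died, yet whether the thrombus killed them is not one of its criteria. The CEC could attribute a death to valve thrombosis and, following the protocol's definition, class the same thrombus as subclinical. Section 12.1 has the CEC classify events according to definitions in the protocol and its charter, so the protocol's wording matters.

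The primary objective (Section 4.1.1) covers the severity of complications as well as their nature and frequency, and valve thrombus is a listed risk in Section 10.1. A severity table that puts a fatal thrombosis in its mildest row understates a device harm. Under Section 13.0 event summaries go to FDA, which approves enrollment in increments of 15 subjects (Section 8.1).

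**Working it through.** The plan gives no thrombosis rate, so there is no figure of its own to reproduce. The check is of the rule's logic, the age of the deciding echo, and the weight of one case.

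**Inputs.** Autopsy rule and gradient criterion: Section 17.1.19. Visit targets and windows: Table 9-2. TTE at each follow-up visit: Section 9.11. Up to 45 treated subjects: Section 8.1.

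**1. Can the cause of death change the class?** Let E be embolism, H new or worsening heart failure, G the last mean gradient and D the discharge gradient (mmHg).

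- E or H present: clinically significant.
- Otherwise, G ≥ 6 and G − D ≥ 5: significant without sequelae.
- Otherwise: subclinical.

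Cause of death is not an argument, so it cannot change the result. Over a grid of D = 1 to 8 and G = 1 to 15 there are 2 × 2 × 8 × 15 = 480 combinations, and switching the thrombus from non-fatal to fatal changes the class in none. With neither E nor H there are 8 × 15 = 120 gradient pairs. The criterion is met in 10 + 9 + 8 + 7 + 6 + 5 + 4 + 3 = 52 of them, leaving 120 − 52 = 68 subclinical. This shows that the class can be reached; it is not a probability.

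**2. Discharge-only echo.** If the discharge echo is the last one, G = D, so G − D = 0, which is below 5. The criterion fails at any gradient. Without E or H every such case is subclinical. The first follow-up window is 30 − 14 = day 16 to 30 + 14 = day 44, so this covers deaths before that visit with no unscheduled echo.

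**3. Age of the last scheduled echo.**

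| Visits (target day) | Gap on target | Largest gap within windows |
|---|---|---|
| 30 to 90 | 60 d | (90+14) − (30−14) = 88 d |
| 90 to 183 | 93 d | (183+14) − (90−14) = 121 d |
| 183 to 365 | 182 d | (365+30) − (183−14) = 226 d |
| 365 to 548 | 183 d | (548+30) − (365−30) = 243 d |

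Later gaps repeat at 182 or 183 days on target and 242 or 243 days at most.

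**4. The heart-failure limb.** The worsening definition needs decongestive therapy to have been stepped up. A subject who dies suddenly may never have had that change. Against this, the autopsy rule admits a diagnosis made after death and covers new as well as worsening failure, and no therapy requirement is attached to new failure. The text can be read either way.

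**5. Neighbouring definitions.** The bleeding scale in Section 17.1.6 has a Fatal class, assigned by adjudicated cause of death. LVOT obstruction in Section 17.1.27 is mixed. On one side, "Cases of intraprocedural LVOTO resulting into death or explant will be considered severe LVOTO". On the other, obstruction found incidentally by pathology is graded on the last available jet velocity, much as thrombus is.

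**6. Weight of one case.** 1/45 = 2.2%. Exact (Clopper-Pearson) 95% intervals: 0/45 gives 0 to 1 − 0.025^(1/45) = 7.9%; 1/45 gives 0.06% to 11.8%.

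**The case against.** The strongest defence is that the route is narrow and the death stays in view. A fatal thrombosis with embolism, or with heart failure recognised before or after death, still reaches the top class. A related fatal thrombosis is a serious adverse event whatever its subclass, and it counts in the primary endpoint (Section 4.2.1) if it falls within 30 days. Every death is adjudicated, and each subject's data are reviewed individually. The thrombus subclass is not a named primary, secondary or exploratory endpoint. All of this stands, and it confines the effect to the severity tabulation and its agreement with the death adjudication.

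A reader might infer that any sudden death from an obstructed valve must come out subclinical because the heart-failure limb cannot be met. The documents do not support that: a postmortem diagnosis is allowed and new heart failure is undefined, so the CEC could reach the top class. A reader might also infer that the CIP treats LVOT obstruction in the opposite way. It does so only for intraprocedural cases; the pathology-discovered case, the closer parallel, also rests on the last echo. The Fatal bleeding class is the sounder comparison.

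The CEC charter, which sets the adjudication algorithm, is not among the documents and might address this. It would not mend the CIP wording. The supplied SAP does not help either: it covers the transapical Pilot Study (CIP-1403), and its device-success definition uses major and minor thrombosis with no mapping from the three EFS classes.

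The size is illustrative. A 243-day gap arises only after month 12 and at the window extremes, and unscheduled echoes would count as available. The case also requires an autopsy, for which only reasonable effort is asked.

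**Conclusion.** The gap is real and narrow. As Section 17.1.19 is written, a thrombus that the CEC holds responsible for a death is classed as subclinical when three conditions coincide: no arterial embolism, no new or worsening heart failure recognised before or after death, and a last echo that misses the gradient criterion. A discharge-only echo always misses it. The result contradicts the CEC's own cause-of-death finding and understates the severity of a device complication. The ambiguous heart-failure limb makes the class depend on interpretation in cases close to this one.

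The size is 2.2 percentage points per case among 45 treated subjects: 0% (0 to 7.9%) reported instead of 2.2% (0.06 to 11.8%). That assumes exactly one such case and all 45 subjects treated; the documents give no basis for a frequency. It also assumes that the charter does not already override the definition. It would be wrong to conclude that the primary endpoint is biased or that deaths go uncounted. The definition should be corrected before thrombus severity is tabulated.

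**What to change.** Add one sentence to Section 17.1.19 and to the CEC charter: *A device thrombus that the CEC adjudicates as causing or contributing to death is classed as clinically significant, regardless of the last available echo.*

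For fatal cases this also removes the dependence on how new heart failure is read and on whether an echo was done after discharge. No further class is needed. The cost is a definition sentence and a charter line, with no new data, since the CEC already adjudicates every death. The downside for the sponsor is that the clinically significant thrombosis figure may become slightly less favourable.

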### 9.9.1 No concomitant procedures are permitted during the index TMVR procedure. Any occurrence will be deemed a protocol deviation.

At the conclusion of the TMVR procedure, the following is assessed via TEE:

- Cardiac function including MR grade
- Paravalvular leak
- Atrial septal defect (ASD) as applicable

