## 9.10 Discharge

Subjects will be cared for through discharge according to standard procedures for mitral valve replacement surgery.

Antithrombotic medication is recommended to be initiated in accordance with local practice and no earlier than Day 1 post-operatively. The recommended post-implant regimen for all subjects

is dual anticoagulation/antiplatelet therapy for a minimum of 6 months with a target INR of 2.5. Dual warfarin and aspirin (81mg) are recommended.

It is also recommended that deep vein thrombosis (DVT) prophylaxis be administered in accordance with local practice for any subject treated, until the INR reaches therapeutic level.

Prior to discharge (or within 14 days post procedure whichever comes first), the following standard exams and tests will be performed:

- Physical exam and review of adverse events and device deficiencies
- Heart Failure Management & Medications
- TTE (addition of TEE evaluation if deemed clinically necessary, or at Investigator discretion)
- 12-lead ECG
- Laboratory tests
  - Creatinine
  - Complete Blood Count
  - Albumin
  - B-type Natriuretic Peptide (BNP) or NT-proBNP
  - INR, if applicable (INR levels to be monitored and reported for all subjects receiving warfarin anticoagulation therapy)
- Multidetector Computed Tomography (MDCT)

Subjects declining the MDCT at time of follow-up or unable to have the assessment will not be considered a protocol deviation

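### A device thrombus first seen at the discharge exam, without embolism or worsening heart failure, cannot meet the rise-from-discharge test on that exam and is classed subclinical at any gradient; before that exam the reference is undefined

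*Combined protocol and SAP*

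**What the plan says.** EFS CIP 17.1.19 sorts device thrombus into three classes.

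- *Clinically significant*: thrombus on imaging "and evidence of arterial embolism or new/worsening heart failure". No gradient test applies.
- *Significant without sequelae* (the middle class): thrombus "in the absence of arterial embolism or new/worsening heart failure, meeting criteria of significant increase in mean gradient", "and warranting initiation or intensification of systemic anticoagulation".
- *Subclinical*: thrombus "in the absence of arterial embolism or new/worsening heart failure and not meeting criteria of significant increase in mean gradient across the implant".

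The asterisked footnote gives the gradient criterion as two limbs joined by AND: a trans-mitral mean Δ of at least 6 mmHg, and at least a 5 "mmHg increase from discharge (10" (the final 10 is a citation number). It names no other reference echo and no rule for a missing discharge echo.

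For thrombus found at autopsy, embolism or heart failure is checked first. If neither is present, the last available echo decides between the other two classes, and the case is subclinical "if last available echo does not meet criteria of significant increase in mean gradient across the implant".

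Section 9.10 fixes the discharge exam: "Prior to discharge (or within 14 days post procedure whichever comes first), the following standard exams and tests will be performed". Its list includes TTE and MDCT. Table 9-1 schedules post-implant MDCT at discharge and at 12 months. The only scheduled post-implant echo before that exam is in Section 9.9.1: "At the conclusion of the TMVR procedure, the following is assessed via TEE". The items named there are cardiac function with MR grade, paravalvular leak and ASD. Mean gradient is not among them.

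**The concern.** A change criterion needs a reference taken before the event it grades. Here the reference exam can also be the exam that finds the thrombus. A high gradient seen together with thrombus at discharge then becomes the subject's own baseline and cannot count as a rise.

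The heart-failure route is only a partial rescue. Worsening heart failure, as defined in 17.1.19, needs both new or progressive symptoms or signs and an unplanned step-up of decongestive therapy. A thrombus with a raised gradient, found on routine imaging before the subject decompensates, is what the middle class exists for, and at the discharge exam it cannot get there.

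The primary objective (4.1.1) covers how severe complications are as well as how often they occur. Section 13.0 has each subject's data reviewed individually, with event summaries sent to FDA, and enrolment is capped at 45. In a study of that size the label on a single thrombus matters.

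**Working it through.** The plan has no figure to reproduce; this is a classification rule, so the check is to apply it as written.

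**Inputs.** g is the mean gradient at the exam being classified and d the mean gradient at discharge (17.1.19 footnote). I read the 6 mmHg limb as an absolute gradient. I also assume that the gradient paired with a thrombus seen at the discharge exam, by TTE or MDCT, is the discharge TTE value.

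**Rule.** The criterion is met if g ≥ 6 and g − d ≥ 5.

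**1. Thrombus first seen at the discharge exam.** Here g = d, so g − d = 0, which is below 5. The criterion fails for every g; trying all values from 0 to 39.9 mmHg gives no success. Without embolism or heart failure, gradients of 6, 10, 15 and 20 mmHg are all subclinical. With either, the same gradients are all clinically significant. Reading the 6 mmHg limb as a change does not alter this result.

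**2. Later exams.** The gradient needed to qualify is the larger of 6 and d + 5:

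| Discharge gradient (mmHg) | Later gradient needed (mmHg) |
|---|---|
| 0 or 1 | 6 |
| 2 | 7 |
| 4 | 9 |
| 8 | 13 |
| 12 | 17 |

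If thrombus has already raised d, the bar rises with it.

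**3. Thrombus found before any discharge echo, or at autopsy in a subject who never had one.** d does not exist, so g − d cannot be formed. The autopsy sentence offers only met or not met. If a discharge echo follows later, literal subtraction runs backwards in time and can even succeed: 12 mmHg before discharge and 4 mmHg at discharge gives 12 − 4 = 8, which is at least 5. The case is undefined, not a certain failure.

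**4. What an earlier reference could change.** Take a discharge gradient of 12 mmHg with visible thrombus. If the end-of-procedure gradient was 3 mmHg (an assumption; the documents give none), the rise is 12 − 3 = 9 and both limbs are met. The same holds for any earlier gradient up to 12 − 5 = 7 mmHg; above 7 mmHg the test still fails.

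**5. Against the rest of the CIP.** A mean gradient of 12 mmHg falls in the severe band of the mitral stenosis table (17.1.30, above 10 mmHg) and exceeds the 5 mmHg at which 17.1.31 counts new stenosis. Under 17.1.19 the same subject's thrombus is subclinical. The LVOT obstruction definition (17.1.27) does handle early events: it measures the increment from baseline, has a rule for intraprocedural cases, and names a fallback echo for pathology findings. Section 17.1.19 has no counterpart.

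**The case against.** A reader might infer that every early thrombus is always filed as subclinical. The text does not support that. Embolism or new or worsening heart failure gives the top class with no gradient test, and the autopsy rule checks for them first. The heart-failure test can be met by symptoms or signs plus an increased oral loop diuretic dose. Failure is also certain only on the discharge exam itself, because a later rise of 5 mmHg over discharge can still qualify. Meeting the gradient test is not enough for the middle class in a living subject either, since anticoagulation must also be warranted.

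A reader might also infer that fatal in-hospital thromboses are hidden, or that the primary endpoint is biased. Neither follows. The primary endpoint (4.2.1) is implant, delivery or device related serious adverse events through 30 days and does not use thrombus subclasses. Death is a serious adverse event by definition and the CEC adjudicates all deaths. High gradients are captured separately through 17.1.30, 17.1.31 and the secondary endpoint on MV stenosis.

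Three further points stand. Discharge MDCT is one of two scheduled post-implant MDCTs, but thrombus may also be seen by echo, and Section 9.11 requires TTE at every follow-up visit, so no share of thrombi can be read from the MDCT schedule. Section 12.1 leaves minimum data and the adjudication algorithm to the CEC charter, which is not in the documents and may already address a missing reference. And the thresholds are cited to an outside source, so dropping the rise limb and using 6 mmHg alone would not be justified from these documents.

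None of this answers the discharge-exam case. There the written rule returns a definite class, and the observed gradient has no influence on it.

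**Conclusion.** The concern holds in a limited form. Without embolism or new or worsening heart failure, a thrombus first seen at the discharge exam is classed subclinical whatever the gradient, and a discharge gradient already raised by thrombus makes later qualification harder. For discharge-exam findings the error can only lower the class. Before any discharge echo the rule is undefined, so a downward bias cannot be claimed for those cases.

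The effect is on severity reporting of thrombus under the primary objective. The documents give no thrombus rate, so the number of affected subjects cannot be estimated; one subject is 1/45 = 2.2% of the maximum enrolment. The SAP supplied is for the transapical Pilot Study (CIP-1403). Its device-success rule uses major and minor thrombosis, so no analysis in it depends on these three classes.

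The discharge-exam result needs no assumed gradient. The later-exam table rests on reading the 6 mmHg limb as absolute. The 3 mmHg example is illustrative only. The point is worth correcting: a stated rule returns a misleading class, and the change needed is small.

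**What to change.** Amend the 17.1.19 footnote and the CEC charter as follows.

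- For thrombus found at or before the discharge echo, measure the rise from the earliest post-implant echo with a recorded mean gradient obtained before the thrombus was seen.
- Where no such echo exists, report the case as gradient change not assessable, list the observed gradient, and do not default it to subclinical. Apply the same wording to the autopsy sentence.
- Keep the discharge reference for thrombus first found later, but flag cases where thrombus was already present at the discharge exam.
- Leave the mmHg thresholds unchanged and do not use the 6 mmHg limb alone.

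The cost is a short text change in two documents. The sponsor must confirm that the end-of-procedure TEE mean gradient is recorded, since 9.9.1 does not list it; if it is not, many early cases will be reported as not assessable. TEE gradients under anesthesia may differ from awake TTE gradients, so the exam used as reference should be listed with each case.
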